Participants will complete rehearsal exercises after every two exposures to ensure there is sufficient content for rehearsal. Learning rate (change in expectancy of an aversive outcome across exposure trials) and relief rate (change in relief ratings across exposure trials) will be calculated based on self-reported expectancy and relief ratings provided after each exposure. We hypothesize that regardless of rehearsal group assignment, participants with reduced baseline reward sensitivity and positive affect will exhibit a slower relief rate relative to individuals with elevated baseline reward sensitivity and positive affect, and that lower positive affect will be associated with lower subsequent relief ratings relative to higher positive affect. We hypothesize that regardless of group assignment, higher relief ratings after the first exposure will be associated with a faster learning rate on subsequent exposure trials. Finally, we hypothesize that the positive rehearsal group will lead to significantly greater reductions in symptoms of social phobia and greater increases in reward sensitivity and positive affect at the end of the study, as well as faster learning and relief rates relative to the neutral rehearsal group.

Research Design & Methods:

Visits will either be conducted over HIPAA-compliant video conferencing platform Zoom or in person.

OVERVIEW

The experiment will consist of two study visits. Visit 1 will include informed consent and questionnaires. Participants will then complete a series of short 1-minute public speaking

exposures. After every two exposures, participants will complete a rehearsal task where the participant is asked to use a positive or neutral approach to remember and recount the exposures they have just completed (for a total of approximately 60-90 minutes). Visit 2 will occur approximately 1 week after Visit 1 and will consist of another series of short 1-minute public speaking exposures, followed by the same rehearsal task after every two exposures. Participants will then be asked to complete another series of questionnaires (for a total of approximately 60-90 minutes) For the rehearsal task in Visits 1 and 2, participant will be randomized to practice rehearsing a) focusing on positive emotional aspects of the exposures, or b) focusing on neutral, factual aspects of the exposures. One week after Visit 2, participants will be asked to complete a brief set of questionnaires (approximately 5-10 minutes).

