Participants will be randomized at the start of the study to a positive or neutral rehearsal group. After every two exposure trials, participants will then complete a rehearsal exercise. Before the rehearsal exercise, participants will complete the visual analog scale to assess current mood. Participants will then be presented with instructions to complete a verbal rehearsal of the two exposures they just completed, followed by a written rehearsal of the two exposures they just completed. After the rehearsal exercise, participants will again rate their current mood using the visual analog scale, US expectancy ratings ("If you were to complete the same exact speech again, how likely is it that the feared outcome would occur?" where 0 = certain the feared outcome will not occur, 50 = completely uncertain, and 100 = certain the feared outcome will occur; and "Did the feared outcome occur?" where 0 = no, and 1 = yes), and relief ratings ("How relieved are you that the feared outcome did not occur?" where 0 = not at all, 50 = moderately, and 100 = very).

This entire process will be repeated four times, resulting in a total of 8 exposure practices and 4 rehearsal exercises. The visit is expected to take approximately 60-90 minutes to complete.

VISIT 2

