After every two exposure trials, participants will then complete a rehearsal exercise (either positive or neutral rehearsal depending on their group assignment). Before the rehearsal exercise, participants will complete the visual analog scale to assess current mood. Participants will then be presented with instructions to complete a verbal rehearsal of the two exposures they just completed, followed by a written rehearsal of the two exposures they just completed. After the rehearsal exercise, participants will again rate their current mood using the visual analog scale, US expectancy ratings ("If you were to complete the same exact speech again, how likely is it that the feared outcome would occur?" where 0 = certain the feared outcome will not occur, 50 = completely uncertain, and 100 = certain the feared outcome will occur; and "Did the feared outcome occur?" where 0 = no, and 1 = yes), and relief ratings ("How relieved are you that the feared outcome did not occur?" where 0 = not at all, 50 = moderately, and 100 = very).

This entire process will be repeated four times, resulting in a total of 8 exposure practices and 4 rehearsal exercises. Participants will then complete a brief set of questionnaires including the LSAS, PRPSA, PVSS, and BAS. The visit is expected to take approximately 60-90 minutes to complete.

FOLLOW-UP

After completion of Visit 2, approximately one week later participants will be sent a short list of questionnaires to be completed independently. Surveys include the public anxiety screening questions, PRPSA, PVSS, and BAS and are expected to take 5-10 minutes to complete.

After completion of the follow-up surveys, participants will be compensated for their time one credit per hour of study participation. All participants will additionally be provided with a referral list at the end of the study.

Statistics & Data Analysis:

Sample size. The sample size will be 74 participants (37 per group). An a priori analysis using G*Power (Faul et al., 2007) indicated that a sample size of 74 would be sufficient to detect a significant effect based on a similar previous study ($d=.30$; Craske et al., 2019) with a power of .80 and an alpha of .05.

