Reward sensitivity and positive affect predicting relief. Linear mixed models will be utilized to assess whether baseline reward sensitivity, measured by the Positive Valence System Scale (PVSS, Khazanov et al., 2020) and the Behavioral Activation Scale (BAS, Carver & White, 1994), and positive affect, measured by a visual analog scale, predict relief rate over the course of exposures. Relief rate will be calculated using a computational model derived from the Rescorla-Wagner model (Rescorla & Wagner, 1972) to capture change in self-reported relief ratings over time. A linear mixed model will also be utilized to assess whether positive affect before an exposure trial predicts subsequent relief on the same trial.

Relief predicting learning rate. A linear mixed model will be utilized to assess whether relief after the first exposure trial predicts learning rate for subsequent exposure trials. Learning rate will be calculated using a computational model derived from the Rescorla-Wagner model (Rescorla & Wagner, 1972) to capture change in self-reported US expectancy ratings over time.

Comparison of positive and neutral rehearsal exercises. A repeated measures between-subjects ANOVA will be utilized to test whether participants in the positive rehearsal intervention show greater reductions in anxiety symptoms (public speaking anxiety screening questions; LSAS, Liebowitz, 1987; PRPSA, McCroskey, 1970) or greater increases in positive affect or reward sensitivity relative to participants in the neutral rehearsal intervention. We will use paired samples t-tests to test whether participants in the positive rehearsal intervention show a faster learning rate or relief rate relative to participants in the neutral rehearsal intervention.

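### The trial-level Aim 1 model (positive affect before a trial predicting relief on that trial) names no group term, although most of its predictor ratings follow randomised rehearsal

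*Combined protocol and SAP*

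**What the plan says.** Statistics & Data Analysis describes three association models for Aims 1 and 2.

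- **Aim 1, baseline predictors.** "Linear mixed models will be utilized to assess whether baseline reward sensitivity, measured by the Positive Valence System Scale", together with the BAS and baseline positive affect, predict relief rate.
- **Aim 1, trial level.** A further mixed model tests "whether positive affect before an exposure trial predicts subsequent relief on the same trial".
- **Aim 2.** Relief after exposure 1 predicts learning rate on later exposures. Specific Aims states the hypothesis as "We hypothesize that regardless of group assignment, higher relief ratings after the first exposure will be associated with a faster learning rate" on later trials.

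No group term is named in any of the three. Group appears only in the arm comparison, for example "A repeated measures between-subjects ANOVA will be utilized to test whether participants in the positive rehearsal intervention show greater reductions in anxiety symptoms".

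Specific Aims also frames the Aim 1 hypotheses as holding whichever arm a participant is in. That covers the link between lower positive affect and lower subsequent relief. The same paragraph predicts that positive rehearsal will raise positive affect and speed up the relief and learning rates.

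On timing, the Visit 1 and Visit 2 sections place a rehearsal after every second exposure, and then: "After the rehearsal exercise, participants will again rate their current mood using the visual analog scale".

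**The concern.** In the trial-level model, randomised group may influence both sides of the regression. Rehearsal is designed to lift mood, and the mood rating straight after it is the latest one before the next exposure. The plan also expects rehearsal to change relief. If the effect on relief does not run wholly through positive affect, group is a common cause of predictor and outcome. A model pooled over arms can then show a positive affect–relief slope with no such relation inside either arm. At stake is the mechanistic reading of that slope: the plan would report it as a link between mood and relief that does not depend on arm.

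**Working it through.** **1. The plan's sample size.** The only input taken from the plan is N = 74, 37 per arm. It was derived from d = 0.30 "with a power of .80 and an alpha of .05". It reproduces as a repeated-measures within-between interaction with f = d/2 = 0.15, 2 groups, 3 occasions, correlation 0.5 and sphericity 1. The last four settings and the conversion to f are assumed, apart from the 2 groups.

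λ = N·m·f²/(1−ρ) = 74 × 3 × 0.0225/0.5 = 9.99, with 2 and 144 degrees of freedom, gives power 0.806.

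The d = 0.30 is not tied to mood ratings or relief, so it does not size the present problem.

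**2. Which predictors precede rehearsal.**

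| Model | Predictor measured | Can group affect it? |
|---|---|---|
| Aim 1, baseline | Before exposure 1, Visit 1 | No |
| Aim 2 | Immediately after exposure 1; first rehearsal follows exposure 2 | No |
| Aim 1, trial level | Before trials 1, 3, 5 and 7 of each visit | Yes, for 7 of 8 ratings |

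The 7 are the three post-rehearsal ratings at Visit 1 (before trials 3, 5 and 7), the three at Visit 2, and the opening Visit 2 rating, which follows four rehearsals. No rating is scheduled directly before the even-numbered trials.

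**3. Predictor before rehearsal.** Group shifts only the outcome, by 0.3 / 0.5 / 0.8 SD. Simulated type I error is 4.7 / 5.0 / 4.9% without group and 4.8 / 5.1 / 4.8% with it. The mean induced correlation is about 0. Omitting group costs only precision: at 0.3 SD it accounts for 0.0225/1.0225 = 2.2% of outcome variance.

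**4. Predictor after rehearsal, one value per person.** With equal arms, both variables shifted by d and no within-arm relation:

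r = 0.25d²/(1 + 0.25d²)

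- d = 0.3: 0.0225/1.0225 = 0.022
- d = 0.5: 0.0625/1.0625 = 0.059
- d = 0.8: 0.16/1.16 = 0.138

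**5. Trial-level version.** This is a simulated random-intercept model with N = 74, eight ratings each, intraclass correlation (ICC) 0.5 and no within-arm relation. The shift is either constant after the first rating or growing. Entries are false-positive rates.

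| Terms in model | 0.3 SD | 0.5 SD | 0.8 SD |
|---|---|---|---|
| No group, no trial | 5–6% | 11–15% | 44–55% |
| Trial effects only | 5% | 7–9% | 19–27% |
| Group × categorical trial | about 5% | about 5% | about 5% |

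Adding only a group main effect to the trial effects leaves 13–14% at 0.8 SD. A linear group-by-trial term left 8.5% at 0.8 SD under a constant shift, which is why trial should be categorical.

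**6. Sensitivity.** With a constant shift and no group term, moving the ICC from 0.3 to 0.7 gives 6–7%, 11–19% and 45–74% at the three shifts. A steeper growing shift, averaging d over the eight ratings and so ending near 2d, gives 34% at 0.5 and 96% at 0.8. Repeat runs differ by a few points.

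**The case against.** Four objections deserve weight.

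- **Silence is not exclusion.** The plan lists no covariates or random effects for any mixed model, and a claim that holds irrespective of arm is compatible with adjusting for arm. This stands. The charge is under-specification, not a decision to leave group out.
- **Mediation.** Background & Significance expects rehearsal to work by raising reward sensitivity and positive affect. If any effect on relief runs wholly through positive affect, the between-arm variation belongs to the mechanism and group does not confound. This stands as a condition on the concern. The plan cannot know it in advance, and in that case adjusting for group would not bias the slope.
- **Direction.** The plan predicts a faster relief rate, not a higher relief level, and Study Description says only that relief will change. Equal shifts in the same direction are therefore an assumption. If the shifts had opposite signs, the induced slope would be negative and could mask a real association.
- **Size.** At 0.3 SD, numerically the plan's only stated effect size, inflation is negligible. The larger rates need shifts that the documents do not give.

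A reader might go further and infer that every Aim 1 and Aim 2 association could be produced by the intervention. The documents do not support that. The baseline measures and the relief rating after exposure 1 precede any rehearsal, and assignment is randomised.

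**Conclusion.** The point holds for one model. As written, the trial-level Aim 1 analysis can report an arm difference as a positive affect–relief association. The false-positive rate is negligibly raised at a 0.3 SD shift on both variables, about 7–15% at 0.5 SD and about 19–55% at 0.8 SD. This rests on an assumed ICC of 0.5, the assumed shape of the shift, and rehearsal acting on relief by some path other than positive affect.

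The baseline Aim 1 model and the Aim 2 model are not biased by omitting group. Two caveats apply. The documents do not say whether participants learn their arm before the first rehearsal. And if the first-exposure predictor were also taken from Visit 2, that rating would follow four rehearsals and the concern would extend to it; the text does not say so. The randomised comparison of rehearsal types is unaffected.

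**What to change.** - **Trial-level Aim 1 model:** specify randomised group, trial as a categorical factor, and group × trial. A group main effect alone is not enough. State which mood rating serves as the predictor for even-numbered trials.
- **Baseline Aim 1 model and Aim 2 model:** add group for a modest gain in precision. To examine whether the association is the same in both arms, add a predictor × group interaction and report it with its confidence interval. With 74 participants, a non-significant interaction would not show equality.

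The cost is a few lines in the analysis plan. Group and trial are already recorded, and no participants, visits or measures are added.

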**Clinical Trials Protocol for “Reward Processes and Rehearsal in Exposure Therapy”
(NCT06132425)**

Last updated and approved on September 26th, 2023
(IRB#23-000236)

Study Description:

The purpose of this study is to 1) examine the importance of self-reported relief following exposure and 2) test whether positive-focused rehearsal following exposure can improve treatment outcomes for participants who endorse fear of public speaking. Exposure therapy is an extinction-based behavioral technique, often employed in the context of cognitive behavioral therapy. It involves strategically exposing an individual to a feared stimulus in an effort to generate new non-fear associations with that stimulus. Relief refers to the positive, rewarding emotions associated with the absence of an expected aversive outcome following exposure to a feared stimulus. In the current study, participants will engage in a series of short public speaking exposures that take place over two sessions. After every two exposures, participants will be asked to complete either a positive or neutral rehearsal exercise, consisting of recalling either positive or neutral aspects of the speech exposures. At multiple points throughout the study, participants will complete ratings of reward sensitivity, positive affect, relief, and expectancy of the aversive outcome. We will test whether 1) participants with higher reward sensitivity and positive affect will report more relief after each exposure, and 2) participants who report experiencing more relief after each exposure will learn more quickly that the feared stimulus does not predict an aversive outcome (i.e., learning rate). We will also test whether participants who engage in the positive rehearsal exercise will show 1) greater reduction in public speaking anxiety symptoms at the end of the study, 2) greater improvements in reward sensitivity and positive affect, and 3) a faster learning rate and changes in relief over the course of the study. The sample will be volunteer UCLA undergraduates who endorse fear and avoidance of public speaking, measured by two Likert scale screening questions. They will come in at two time points: Visit 1 (first set of exposures) and Visit 2 (second set of exposures), and will complete a few short surveys one week after Visit 2.

Background & Significance:

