Treatment response rates for cognitive behavioral therapy (CBT) across anxiety disorders average approximately 50% post-treatment and at follow-up (Loerinc et al., 2015). Thus, recent research has amplified efforts toward improving treatment methodology in an attempt to optimize clinical outcomes. Many efforts have targeted exposure therapy, an evidence-based behavioral technique during which a participant is strategically and repeatedly exposed to a feared stimulus in order to generate new non-fear associations with that stimulus.

Mechanisms of exposure therapy have been conceptualized using inhibitory retrieval models of extinction learning. These models, derived from Pavlovian conditioning, posit that extinction is dependent upon formation of an inhibitory association where the feared conditional stimulus (CS) no longer predicts the aversive unconditional stimulus (US). The new inhibitory CS-noUS association then competes with the original CS-US association. Research has demonstrated that greater expectation of US occurrence (US expectancy) followed by the unexpected omission of the US (i.e., expectancy violation) is associated with greater learning of the inhibitory association (Bouton, 1993). Exposure therapy is a clinical proxy of extinction; in order to compete with the original association between public speaking (CS) and rejection (US), participants engage in repeated exposures to the CS without the US (no rejection) and form a

new inhibitory association wherein public speaking no longer predicts rejection (Craske et al., 2022). Strategies to enhance this inhibitory learning process include mental rehearsal, where information from a previous exposure trial is recounted to reinforce the newly learned inhibitory association (McGlade & Craske, 2021).

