There is also promising evidence which suggests that reward processes may facilitate extinction learning, though studies have yet to be conducted in a clinical sample. Experimental studies have demonstrated that greater relief, a positive emotion that occurs following US omission, is associated with greater expectancy violation (San Martín et al., 2020; Vervliet et al., 2017; Willems & Vervliet, 2021). This suggests that positive emotions during exposure (e.g., relief) may directly influence the extinction learning process. Reduced positive affect has been associated with decreased updating of US expectancies, leading to slower learning during extinction (Young et al., 2021). In contrast, elevated positive affect has been associated with enhanced encoding, rehearsal, and retrieval processes, which may lead to faster learning during extinction and prevent return of fear (i.e., relapse) (Zbozinek & Craske, 2017). Strategies designed to enhance reward sensitivity and positive affect may therefore be an important avenue of future research to improve exposure therapy outcomes. While not yet applied during exposure, strategies aimed to increase reward sensitivity via positive-focused rehearsal have led to decreased anxiety, depression, and negative affect and increased positive affect (Chen et al., 2021; Craske et al., 2019, *in press*; A. Waters et al., 2016; L. Waters & Stokes, 2015). Recent work has shown that rehearsal without a positive focus immediately following exposure leads to reductions in anxiety (McGlade & Craske, 2021). Therefore, rehearsal following exposure that specifically focuses on positive emotions to increase reward sensitivity has the potential to lead to even greater symptom improvement.

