The current research specifically aims to examine the role of relief during extinction learning and to test whether positive-focused rehearsal exercise may be implemented to improve treatment outcomes in exposure therapy in a population of individuals who demonstrate excessive fear of public speaking. This is a highly relevant population, given that the National Comorbidity Survey Replication estimated that 13% of Americans are estimated to experience social phobia at some point in their lives (Kessler et al., 2012). Further, a more recent study assessed over 1100 college students and 63.9% reported a fear of public speaking (Ferreira Marinho et al., 2017). The current study has three primary aims. First, the study seeks to examine whether baseline reward sensitivity and positive affect predict relief following exposure. Second, the study seeks to examine whether relief predicts subsequent extinction learning across exposure trials. Third, the study seeks to test the efficacy of a positive rehearsal exercise following exposure, characterized by technology-guided recall and rehearsal of positively-valenced emotional aspects of speech exposures done in session, relative to a neutral rehearsal exercise following exposure, characterized by technology-guided recall and rehearsal of non-emotional, factual aspects of speech exposures done in session.

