Eligibility Questionnaire
Demographics Questionnaire

Liebowitz Social Anxiety Scale (LSAS, Liebowitz, 1987)

Personal Report of Public Speaking Anxiety (PRPSA, McCroskey, 1970)

8-item version (excluding the suicide item) of the Patient Health Questionnaire-9 (PHQ-9, Kroenke et al., 2001)

Positive Valence System Scale (PVSS, Khazanov et al., 2020)

Behavioral Activation Scale (BAS, Carver & White, 1994)

Visual Analog Scale (adapted from Lang, 1980)

All participants will then engage in a series of exposure practices. They will undergo 8 exposure trials for durations of 1 minute each. Prior to the first exposure, participants will be asked to record their feared negative outcome (i.e., unconditioned stimulus [US]), such as social rejection, to be used for reference during future US expectancy and relief ratings. During each exposure trial, they will first complete self-reported current fear/anxiety ratings ("How fearful and anxious are you right now about giving this speech?" where 0 = not at all, 50 = moderately, and 100 = very) and US expectancy ratings ("How likely is it that the feared outcome will occur?" where 0 = certain the feared outcome will not occur, 50 = completely uncertain, and 100 = certain the feared outcome will occur). Participants will then have 10 seconds to look at a speech topic followed by one minute of giving this speech to an audience of two confederates. Immediately after the exposure, participants will complete self-reported current fear/anxiety ratings ("How fearful and anxious are you right now after giving this speech?" where 0 = not at all, 50 = moderately, and 100 = very), US expectancy ratings ("If you were to complete the same exact speech again, how likely is it that the feared outcome would occur?" where 0 = certain the feared outcome will not occur, 50 = completely uncertain, and 100 = certain the feared outcome will occur; and "Did the feared outcome occur?" where 0 = no, and 1 = yes), and relief ratings ("How relieved are you that the feared outcome did not occur?" where 0 = not at all, 50 = moderately, and 100 = very). Participants will then be given another speech topic and will follow the same procedure.

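### Does Aim 2 need adjustment for starting expectancy and for reported occurrence of the feared outcome?

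*Combined protocol and SAP*

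**What the plan says.** Specific Aims lists three primary aims, of which this is one: "Second, the study seeks to examine whether relief predicts subsequent extinction learning across exposure trials". The hypothesis there is that "higher relief ratings after the first exposure will be associated with a faster learning rate on subsequent exposure trials". Under Statistics & Data Analysis, the paragraph on relief predicting learning rate gives one linear mixed model. Trial-1 relief is the predictor, later learning rate is the response, and no covariate is named. Learning rate comes from a model derived from Rescorla-Wagner and fitted to the expectancy ratings. Its start value and outcome term are not spelled out.

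VISIT 1 and VISIT 2 give the ratings. Expectancy is rated before each speech. Straight after it, participants rate expectancy again, answer "Did the feared outcome occur" (0 or 1) and then answer "How relieved are you that the feared outcome did not occur" (0 to 100). No skip or recoding after a yes is described. The items return after every second speech: "After the rehearsal exercise, participants will again rate their current mood using the visual analog scale, US expectancy ratings", followed by the 0/1 and relief items. At Visit 2 the feared outcome is recorded afresh.

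**The concern.** The protocol's own theory suggests common causes of predictor and response. The Study Description says "Relief refers to the positive, rewarding emotions associated with the absence of an expected aversive outcome". Background & Significance says that "greater expectation of US occurrence (US expectancy) followed by the unexpected omission of the US (i.e., expectancy violation) is associated with greater learning", and also that "greater relief, a positive emotion that occurs following US omission, is associated with greater expectancy violation". Someone who starts with high expectancy may therefore report more relief and also learn differently, even if relief itself does nothing.

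Occurrence adds a second route. After a yes, the relief item asks about something that did not happen, so a low score may only mark that the outcome occurred. People who often report occurrence would then have low relief and, under some scorings, a low learning rate as well.

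At stake is whether a primary-aim result could be an artefact of scoring, with a sign that depends on choices the plan does not state. Both candidate covariates are already collected. The randomised comparison is not affected.

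**Working it through.** **1. The plan's own figure.** The plan has no sample-size figure for Aim 2. The stated 74 is reproduced by the group-by-time interaction of a repeated-measures ANOVA with f = d/2 = 0.15, m = 3 measurements and correlation 0.5 (the last two are assumptions): lambda = f² × N × m/(1 − rho) = 0.0225 × 74 × 3/0.5 = 9.99, power 0.806. For one predictor at N = 74, the correlation detectable with 80% power is tanh((1.960 + 0.842)/√71) = 0.32.

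**2. Which scoring the text supports.** Specific Aims says the rates use ratings given after each exposure, which points to the immediate answers and not the post-rehearsal repeats. The analysis section speaks of change in self-reported ratings, which points to each person's own start. The visit sections list the 0/1 item among the expectancy ratings, and a Rescorla-Wagner model needs an outcome term. I call this the natural reading.

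**3. Why the scoring matters.** The update is V(next) = V + a(outcome − V). Assume a = 0.31 for everyone and starting expectancy with mean 65, SD 18. One speech with omission leaves 0.69 × V.
- Starts of 83, 65 and 47 give 57.27, 44.85 and 32.43 after exposure 1. The next omission takes the first and last to 39.52 and 22.38.
- Own start: 1 − 39.52/57.27 = 0.31 and 1 − 22.38/32.43 = 0.31. Starting level drops out.
- Common start of 44.85: 1 − 39.52/44.85 = 0.12 and 1 − 22.38/44.85 = 0.50. High starters look slow, so the false association with relief is negative.
- Occurrence at V = 44.85: the next value is 44.85 + 0.31 × 55.15 = 61.95. With the reported outcome, 17.10/55.15 = 0.31. Scored as an omission, (44.85 − 61.95)/44.85 = −0.38. People who report occurrence look slow, so the false association is positive.

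**4. Simulation with no true link.** There were 74 people, 8 trials and 2,000 runs per cell. Rates were Beta(4,9) and rating noise had SD 8. Relief was 50 + slope × (expectancy − 65) with noise SD 15, or about 0 or 30 after a yes. Occurrence was 5, 10 or 20%, with weak (ICC 0.09) or strong (ICC 0.33) clustering by person. With one rate per person the mixed model reduces to regression. All inputs are assumptions.

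| Scoring | Unadjusted rejection (nominal 5%) |
|---|---|
| Natural reading | 4.0–7.1% |
| Post-rehearsal answer for exposures 2, 4, 6, 8; weak clustering, relief near 0 | 6–7 / 9–10 / 12–17% at 5/10/20% occurrence |
| All trials scored as omissions; strong clustering, relief near 0 | 16 / 25–27 / 42% at 5/10/20% |
| All trials scored as omissions; weak clustering | 4–8% |
| Common start, no occurrence | 12 / 20 / 49% at slopes 0.2/0.3/0.6 |
| Common start and all omissions | 4–58%, either sign |

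Repeats of the natural reading with fewer runs fell between 2.9% and 7.1%. The simulation standard error at 5% is √(0.05 × 0.95/2000) = 0.5 points, so the highest cells carry a real excess, but only of about 2 points. Dropping people with a trial-1 yes gave 4.9–6.5%. Fitting both visits gave 3.8–9.2% as one chain and 4.1–7.6% with a restart at Visit 2.

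**5. If starting expectancy does drive learning.** With an assumed correlation of 0.3 between rate and starting expectancy, the natural reading rejects in 7–22% of runs unadjusted and 4.6–5.2% adjusted. A purely correlational calculation has the same structure: the induced relief–learning correlation is the product of the two links, 0.3 × 0.3 = 0.09 up to 0.5 × 0.5 = 0.25, with rejection of 12% to 59%. In these cases relief really does predict learning; what is open is why.

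**6. Price of the covariates.** On the natural reading the standard error of the relief coefficient grew 1.0- to 1.7-fold. With a simulated link of r = 0.35 following total relief, power fell from 62–68% to 33–50%. A repeat gave 63–65% falling to 34–42%. If learning instead follows relief beyond expectancy and occurrence, power moved from 30–57% to 55–62%.

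**The case for a change.** The strongest case for a change is that the plan does not commit to the natural reading. The alternatives bias in opposite directions, and two covariates already in hand bring rejection back to 3.4–6.8% in the main simulation (8.1% in one repeat cell). They would also guard against a link between starting expectancy and learning, which the Background itself suggests. It would cost a few sentences and no new data.

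Part of this stands. The start value, outcome term, handling of the two visits and treatment of relief after a yes are not written down. The Study Description also refers loosely to relief after each exposure, while the hypothesis and the analysis section agree on the first.

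The rest is weaker. The alternative scorings fit the text poorly: a shared start value is an odd way to measure individual change, and scoring every trial as an omission would ignore an item collected on every trial. The documents give no frequency of yes answers and describe exposures as taking place without the feared outcome. The highest all-omission figures need 20% occurrence, strong clustering and near-zero relief together. Under the natural reading, adjustment matters mainly if learning depends on starting expectancy, and no size is given for that. Even then, the aim is worded as prediction. Because the protocol ties relief to expectancy violation, conditioning on expectancy may remove part of what is being studied.

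**Conclusion.** No change to the plan follows. On the scoring the text best supports, and if learning rate is unrelated to starting expectancy, the unadjusted test runs at about 3% to 7% against a nominal 5%. Large distortions arise only under scorings the plan does not state. The unspecified model inputs are a gap that a competent analyst would fill sensibly and describe when reporting, together with counts of yes answers.

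The covariates are a fair trade-off and do not correct an error. They answer whether relief predicts learning beyond expectancy and occurrence. They may raise power if that is how learning works, or cost about a third to a half of it if total relief is what counts (in the repeat, 1 − 42/63 = 0.33 to 1 − 34/65 = 0.48). The adjusted model is a reasonable optional supporting analysis, and the unadjusted association remains a proper test of the aim as worded. This rests on assumed occurrence rates, relief slopes and noise, and on regression standing in for the mixed model.
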